The primary outcome will also be analysed by the proportion of patients with these clinical syndromes that are seen within a clinically appropriate timeframe (defined as 15 minutes, as discussed below).

Secondary outcomes will include:

- Length of hospital stay
- ED mortality
- Inpatient mortality

These are also defined in Appendix 3.

Secondary objectives

Validity of the WHOTS will be assessed through its ability to predict ED outcomes. This will include the relationship between triage category and admission rates and ED mortality.

Under- or over-triage rates will also be calculated using disposition as a reference standard. This approach has limitations (see below) but is widely used in triage research.

Over-triage will be defined as the proportion of emergency (category 1) patients who are discharged. Under-triage will be defined as the proportion of non-urgent (category 3) patients who are admitted. Rates will be compared with the acceptable under- and over-triage rates recommended by ACS COT¹³ (and widely referenced in triage research) and then benchmarked against other published data. This approach has limitations (given that not all category 1 patients will require admission, and many category 3 patients could reasonably be expected to; recommendations for triage in trauma do not necessarily apply to other disease categories; and the performance targets provided by an American society do not necessarily apply to other contexts) but will be undertaken to enable comparison with other triage research from LMICs.

Reliability will be assessed through inter-rater agreement between two local triage nurses as well as a local nurse and independent expert triage nurse.

Analysis

All data will be obtained from the MHPH medical records database. Hospital medical records staff will export de-identified data into an Excel document, which will be provided to researchers and stored on a secure, password protected Monash University drive. All data will be analysed using Stata. No identifiable data will be available to the researchers.

Primary objectives

For the primary outcomes, Student's t-test will be used to compare the difference in TTA for the ten sentinel conditions (assuming parametric data). Chi-Square will be used to determine the difference in proportions of patients seen within 15 minutes.

For the secondary outcomes of ED mortality, hospital mortality and hospital LOS, Student's t-test or Chi-Square will be used as appropriate.

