Secondary objectives

For predictive validity, Chi-Square and correlation coefficient derived by Cramer's V will be used to investigate the relationship between triage category and admission rates & ED mortality.

Under- and over-triage rates will be calculated using the definitions above. Acceptable limits set by the American College of Surgeons Committee on Trauma (an under-triage rate of less than 10% and an over-triage rate of 30–50%) will be used as the reference standard.¹³ This approach is consistent with that used in other triage research, despite the limitations discussed above.^{9–12}

For reliability, the modified Kappa statistic will be used to test inter-rater agreement between triage nurses.

Sample size

It is estimated that approximately 15 patients per day present with one of the ten sentinel syndromes and wait an average of 20 minutes to be seen. A clinically significant improvement in the TTA for these patients is thought to be five minutes. Although Australasian guidelines recommend that high acuity presentations (equivalent to categories one and two in the Australasian Triage Scale) are seen within 10 minutes of arrival,¹⁶ a target of 15 minutes is thought to be acceptable in the resource limited context of MHPH.

Based on these figures, a sample size of 34 (17 per group) will be required to demonstrate a clinically significant decrease in TTA for the selected time-critical conditions at an alpha of 0.05 and beta of 0.8.

The primary outcome will also be analysed by the proportion of patients seen within 15 minutes of arrival. Assuming baseline performance is 45%, an absolute improvement of 10% (to 55%) will require a sample size of 784 (392 per group) at an alpha of 0.05 and beta of 0.8.

The secondary outcome of mortality will require a larger sample. In order to demonstrate an absolute reduction in mortality of 5% (from an estimated baseline mortality rate of 15%), a sample size of 1372 (686 per group) is required at an alpha of 0.05 and beta of 0.8.

To ensure a satisfactory sample size to demonstrate all outcomes, pre- and post-intervention periods of 8 weeks will be utilised. This is based on a total sample size of 1372 for the secondary outcome of mortality (with a buffer of 10%) at an estimated presentation rate of 15 per day. This requires pre- and post-intervention periods of at least 50 days.

Ethics

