Ethics approval, including a waiver of consent, will be sought from Monash University. Consistent with local processes, approval to conduct this research will then be sought from the Medical Research Advisory Committee within the Papua New Guinean National Department of Health.

Limitations

This study has been designed to ensure it is methodologically robust. There are, however, several limitations that will need to be considered when interpreting the results.

The pre-post nature of the design means that the study may be subject to confounding. A particular risk is that a new and efficient triage system may prompt an increase in ED presentations, and a change in the overall acuity of the patient cohort. For this reason, the primary outcome will focus on ten clearly-defined time critical conditions.

Other factors may also influence the primary outcome, such as changes in staffing levels and acute fluctuations in demand for emergency care (for instance, in the setting of disaster or outbreak). Within the influence of the researchers, attempts will be made to control these factors and minimise variation across the study period.

There is a risk that the study will be subject to the Hawthorne effect. Although treating clinicians will be blinded to the primary outcome, they will have knowledge of the ten sentinel conditions by virtue of their inclusion on the PTRF. It is therefore possible that patients presenting with these syndromes will be prioritised for care.

These limitations reflect the real-world challenges of conducting research in developing settings. The proposed study design is an attempt to balance methodological rigour with the practical considerations of emergency care delivery and research at MHPH.

Conclusion

Triage is an essential component of EC systems, especially in developing settings where demand for care typically exceeds the available resources. This study, using pre-post intervention methodology, will determine whether the introduction of a triage system leads to a clinically significant decrease in TTA for selected time-critical syndromes. It will also describe the impact on ED mortality, hospital mortality and total LOS.

A secondary objective of this study is to assess the validity and reliability of the WHO triage scale. There is currently no published data on the performance of this system.

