Appendix 1A – Pre-intervention Patient Registration and Triage Form

Appendix 1B – Post-intervention Patient Registration and Triage Form

See attached.

Appendix 2

World Health Organization Triage Scale – user guidance

See attached.

Appendix 3

Definitions for primary and secondary outcomes

Definitions related to primary outcomes

- Major trauma – any injury requiring blood transfusion or an intercostal catheter in the ED, or transfer direct to the operating theatre
- Severe head injury – any patient with objective evidence of a head injury and a Glasgow Coma Scale less than nine
- Major burns – any burn of greater than 15% total body surface area, as estimated by the treating clinician
- Myocardial infarction – an ECG positive for ST-elevation myocardial infarction, or raised troponin based on the threshold defined by the local laboratory
- Septic shock - fever (temperature $>37.5^{\circ}\text{C}$) and hypotension (systolic BP $\leq 90\text{mmHg}$)
- Ruptured ectopic pregnancy – objective evidence of pregnancy (extra-uterine gestational sac on ultrasound or positive urine βHCG) and free fluid on ultrasound
- Severe asthma/COPD – any patient with an oxygen requirement where the most likely diagnosis is an exacerbation of asthma or chronic obstructive pulmonary disease
- Severe pneumonia – any patient with an oxygen requirement where the most likely diagnosis is pneumonia
- Meningitis – any patient where the most likely clinical diagnosis is meningitis
- Appendicitis - any patient where the most likely clinical diagnosis is appendicitis

Time to assessment - the time interval in minutes between patient arrival at ED reception and the time of first assessment by the treating clinician

Definitions related to secondary outcomes

- Length of hospital stay – the number of days from presentation to discharge
- ED mortality – any death that occurs while the patient was physically in the ED, excluding patients who meet criteria for ‘deceased on arrival’
- Inpatient mortality - any death that occurs while the patient was admitted to hospitals, excluding any deaths that occur in the ED

Deceased on arrival is defined as any patient who is obviously deceased on arrival, as determined by the treating clinician.

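### The 8-week periods rest on one power calculation for undivided mortality, but the plan tests two non-overlapping death outcomes, so the 80% power is shown for at most one of them

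*Combined protocol and SAP*

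**What the plan says.** The Sample size section treats mortality as a single secondary outcome: "In order to demonstrate an absolute reduction in mortality of 5% (from an estimated baseline mortality rate of 15%), a sample size of 1372", that is 686 per group. It adds a 10% buffer and converts patients to days "at an estimated presentation rate of 15 per day". The same section gives that rate for sentinel presentations: "approximately 15 patients per day present with one of the ten sentinel syndromes". No admission fraction is applied. It concludes: "To ensure a satisfactory sample size to demonstrate all outcomes, pre- and post-intervention periods of 8 weeks will be utilised".

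The Outcomes section lists ED mortality and inpatient mortality separately. Appendix 3 defines the first as "any death that occurs while the patient was physically in the ED", leaving out patients deceased on arrival. It defines the second as death while admitted, "excluding any deaths that occur in the ED". The Analysis section assigns tests to each: "For the secondary outcomes of ED mortality, hospital mortality and hospital LOS". The Post-intervention section takes inpatient deaths from the medical records of admitted patients. The Conclusion is more modest: "It will also describe the impact on ED mortality, hospital mortality and total LOS".

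**The concern.** The outcome that sets the study length is one undivided mortality rate, and the outcomes tested are two separate parts of mortality. No outcome that adds the parts together is listed, defined or tested. Neither part has its own baseline rate or expected reduction, and the denominator for inpatient mortality (all sentinel patients, ED survivors or admitted patients) is not given.

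Two things are at stake. First, a reader told that the study can demonstrate all outcomes may take a non-significant ED or inpatient result as evidence of no effect, when the plan has not shown that the test could detect one. Second, the intervention changes patient flow, so the place of death could shift between ED and ward. Two separate outcomes do not by themselves tell the reader whether total deaths changed.

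**Working it through.** **Inputs from the Sample size section:** 15% to 10%; alpha 0.05, taken as two-sided; the stated beta of 0.8 read as 80% power; 15 patients per day; 10% buffer; 8 weeks per period.

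**1. The plan's own figure.** With pooled variance under the null, n per group = [1.960 × √(2 × 0.125 × 0.875) + 0.842 × √(0.15 × 0.85 + 0.10 × 0.90)]² / 0.05² = (0.9167 + 0.3925)² / 0.0025 = 685.6, so 686 per group and 1372 in total. Duration: 1372 × 1.1 / (2 × 15) = 50.3 days, which agrees with the stated minimum of 50. Eight weeks give 56 × 15 = 840 per period. One outcome falling from 15% to 10% has 80.0% power at 686 and 87% at 840.

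The documents do not say which deaths the 15% covers, so the readings below are assumptions. All use 840 presentations per period and power = Φ[(difference − 1.960 × SE pooled) / SE unpooled].

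**2. If 15% is all deaths and each part falls by one-third.** Let e be the ED baseline rate. ED mortality goes from e to 2e/3 on 840. Inpatient mortality among ED survivors goes from (0.15 − e)/(1 − e) to (2/3)(0.15 − e)/(1 − 2e/3).

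Worked case, e = 7.5%. ED: 7.5% to 5%, SE pooled = √(2 × 0.0625 × 0.9375/840) = 0.01181, SE unpooled = √((0.075 × 0.925 + 0.05 × 0.95)/840) = 0.01180, so Φ[(0.025 − 0.02315)/0.01180] = Φ(0.157) = 56%. Inpatient: 8.11% of 777 survivors to 5.26% of 798, giving 62%.

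| ED / inpatient baseline, % of all patients | ED power | Inpatient power, ED survivors | Inpatient power, all patients |
|---|---|---|---|
| 3 / 12 | 26% | 80% | 78% |
| 5 / 10 | 40% | 73% | 70% |
| 7.5 / 7.5 | 56% | 62% | 56% |
| 10 / 5 | 70% | 46% | 40% |

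The combined test has 87% power in every row.

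**3. If 15% is inpatient mortality among admitted patients.** The calculation then needs 686 admitted patients per period, and 686/840 = 82% of presentations. Power is 80% at that share, 84% at 90% admitted (756 patients) and 59% at 50% admitted (420 patients). Nothing is shown for ED mortality.

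**4. If 15% is all deaths and the whole 5-point fall is in one part.** With all patients as denominator, the test of that part has 94% power from 12% to 7%, 97% from 10% to 5%, and over 99% from 7.5% to 2.5%. The combined test stays at 87%.

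**The case against.** The best defence is that the 15% may be the baseline for one of the listed outcomes, most plausibly inpatient mortality. The sentinel definitions in Appendix 3 are severe, so most of these patients may be admitted, and presentations could then stand in roughly for admissions. That possibility stands. A reader might infer that the calculation belongs to no tested outcome, or that 15% must mean all deaths because no admission fraction was applied. The documents support neither inference: they leave the matter open.

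A second defence is that the low power figures come from spreading the benefit over both parts. This also stands. Triage acts at arrival, and if the reduction is concentrated in one place, the separate test of that part does better than a combined test. A reader might conclude that both mortality tests are underpowered; the documents do not establish that.

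A third is that 15% to 10% was meant for each outcome in turn. The section speaks of one outcome with one rate, and that reading would put total deaths at 15% + 0.85 × 15% = 27.75% before the change, which the plan nowhere says.

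Finally, these are secondary outcomes and the Conclusion promises only description. That limits the consequence. It does not remove the point, because mortality sets the length of the study, formal tests are assigned, and the Sample size section claims that all outcomes can be demonstrated.

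**Conclusion.** The mismatch is certain from the text: one mortality outcome is sized, two mutually exclusive ones are tested, and the link between them is missing. The stated 80% power is therefore shown for at most one tested death outcome, and the claim covering all outcomes is too broad for mortality.

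The size of any loss is not known. It depends on the ED/ward split, the admitted share and where the benefit falls, none of which the plan gives. Under an equal relative reduction, at least one of the two tests is below 80% in every split shown, with a lowest value of 26% (40% if inpatient deaths are taken over all patients does not go lower). Under a concentrated reduction, the affected part is well powered. These are illustrations, not findings about this study.

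A shift of deaths from ED to ward with an unchanged total would be a real change in both components. A reader might treat a significant component in that setting as a false positive; it is not one. It is only a reason to report the total as well. The primary outcome is unaffected, and the point should be fixed.

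**What to change.** - Add a secondary outcome to the Outcomes list and Appendix 3, before outcome data are examined: death in the ED or before hospital discharge, excluding deceased on arrival, with all sentinel-condition patients as denominator in both periods. Patients discharged alive from the ED count as survivors.
- If 15% is that rate, tie the 1372 calculation to this outcome. If not, name the outcome and denominator it belongs to and restate the power.
- Keep ED and inpatient mortality as components, each with a stated denominator and no separate power claim.
- Limit the sentence about all outcomes to those actually powered, and use the term inpatient mortality where the Analysis and Conclusion sections say hospital mortality.

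The cost is small. ED and inpatient deaths are already planned outcomes, and admitted patients are already identified by hospital number, so no new data are needed. If 15% is the combined rate, the study length stands; otherwise the baseline must be re-estimated. The separate tests lose their implied power claim, and the combined test is the weaker one if the benefit falls wholly in one place.

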Appendix 1A – Pre-intervention Patient Registration and Triage Form

Appendix 1B – Post-intervention Patient Registration and Triage Form

See attached.

Appendix 2

World Health Organization Triage Scale – user guidance

See attached.

Appendix 3

Definitions for primary and secondary outcomes

Definitions related to primary outcomes

- Major trauma – any injury requiring blood transfusion or an intercostal catheter in the ED, or transfer direct to the operating theatre
- Severe head injury – any patient with objective evidence of a head injury and a Glasgow Coma Scale less than nine
- Major burns – any burn of greater than 15% total body surface area, as estimated by the treating clinician
- Myocardial infarction – an ECG positive for ST-elevation myocardial infarction, or raised troponin based on the threshold defined by the local laboratory
- Septic shock - fever (temperature $>37.5^{\circ}\text{C}$) and hypotension (systolic BP $\leq 90\text{mmHg}$)
- Ruptured ectopic pregnancy – objective evidence of pregnancy (extra-uterine gestational sac on ultrasound or positive urine βHCG) and free fluid on ultrasound
- Severe asthma/COPD – any patient with an oxygen requirement where the most likely diagnosis is an exacerbation of asthma or chronic obstructive pulmonary disease
- Severe pneumonia – any patient with an oxygen requirement where the most likely diagnosis is pneumonia
- Meningitis – any patient where the most likely clinical diagnosis is meningitis
- Appendicitis - any patient where the most likely clinical diagnosis is appendicitis

Time to assessment - the time interval in minutes between patient arrival at ED reception and the time of first assessment by the treating clinician

Definitions related to secondary outcomes

- Length of hospital stay – the number of days from presentation to discharge
- ED mortality – any death that occurs while the patient was physically in the ED, excluding patients who meet criteria for ‘deceased on arrival’
- Inpatient mortality - any death that occurs while the patient was admitted to hospitals, excluding any deaths that occur in the ED

Deceased on arrival is defined as any patient who is obviously deceased on arrival, as determined by the treating clinician.

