MHPH is the city's major health facility. There is limited primary care infrastructure within the province, so patients rely on MHPH for the majority of their healthcare needs. As in other parts of the country, there is a large burden of both communicable and non-communicable disease, including HIV/AIDS, tuberculosis diabetes, cardiovascular disease, chronic respiratory conditions and trauma.

The ED receives approximately 150 presentations per day, and is staffed by one emergency physician, three registrars (specialists in training), five health extension officers (HEOs) and approximately thirty nurses. The ED has recently been redeveloped, and now includes four resuscitation bays, 16 acute beds and five short-stay beds. Basic pathology and radiology services are available.

Under current arrangements, the ED has no triage system and manual data collection processes are leading to gross under-reporting of presentation numbers. Major challenges for the ED include understaffing, a large burden of primary care patients and access block.

A new electronic database of ED patients has recently been implemented to capture basic attendance data. This system will facilitate data capture for the study.

Design

This study will utilise pre-post intervention methodology and will be prospectively registered as a clinical trial with the United States National Library of Medicine Clinical Trials Register at clinicaltrials.gov.

Pre-intervention

A new MHPH ED Patient Registration and Triage Form (PRTF) will be created to facilitate the new system and capture relevant data items, such as demographics and initial vital signs (Appendix 1). This form will be based on an existing MHPH ED discharge form, as well as a triage form successfully implemented in another Pacific setting.⁷

Data from the PRTF will be entered by ward clerks into the ED's electronic patient registration system (recently implemented as part of a hospital-wide data improvement project). This system forms part of the MHPH medical records database.

After a trial period of staff testing the new form, the PRTF will be implemented and baseline data captured in the database. During this period, the PRTF will not include any triage information (Appendix 1A). Based on a power calculation (see below), two months of pre-intervention data will be collected.

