In order to identify patients who meet inclusion criteria, as defined below, the PRTF will require the treating clinician to indicate whether the patient had one of the ten sentinel conditions (listed below).

Intervention

The intervention will comprise implementation of a new triage and patient flow system facilitated through staff training and clinical redesign.

The three-tier World Health Organization Triage Scale (WHOTS) will be used as the triage instrument. This tool, developed collaboratively by the WHO, International Committee of the Red Cross (ICRC) and Médecins Sans Frontières (MSF), incorporates features of the SATS but has been modified for application in a wide variety of RL settings. WHOTS documents are provided in Appendix 2.

At the end of the baseline data collection period, MHPH ED staff will be trained in the new system. A variety of ED clinicians (who will subsequently take on the triage role) will be the focus of this training program. This will include nurses, community health workers and health extension officers in order to provide flexibility in the staffing model. Triage training will be delivered by an experienced Australasian volunteer nurse(s) and comprise workshops on triage principles, paper-based scenarios and simulation exercises.

Signage will be introduced to facilitate the new system of flow, and the ED will begin utilising the version of the PRTF that incorporates triage data (Appendix 1B). The triage instrument will be piloted over a one-month period (approximately). Modifications will be made based on real-time feedback as well as observations by the visiting team.

Post-intervention

After completion of the trial period, the new triage and flow system will be implemented under the leadership of local clinicians. The ED registration database will be updated to capture triage category data.

For admitted patients, hospital length-of-stay (LOS) and inpatient mortality data will be obtained from the WHPHA medical records database. These patients will be identified by the patient's unique hospital identification number.

Outcomes

Primary objective

The primary outcome will be time-to-assessment (TTA) by an ED clinician for ten time-critical conditions:

- Severe trauma
- Major burns
- Severe head injury
- Ruptured ectopic pregnancy
- Septic shock
- Myocardial infarction
- Severe asthma/COPD
- Severe pneumonia
- Meningitis
- Appendicitis

Pragmatic definitions for these conditions are provided at Appendix 3.

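### The septic shock definition uses one blood-pressure cut-off for all ages and no diagnostic clause, so febrile young children with pressure normal for their age could meet it.

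*Combined protocol and SAP*

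**What the plan says.** Appendix 3 (definitions related to primary outcomes) gives two elements for septic shock: "Septic shock - fever (temperature $>37.5^{\circ}\text{C" and then "and hypotension (systolic BP $\leq 90\text{mmHg". There is no age band and no mention of infection or of a working diagnosis. Asthma/COPD, pneumonia, meningitis and appendicitis are handled differently in the same list. Pneumonia, for example, is "any patient with an oxygen requirement where the most likely diagnosis is pneumonia".

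The text sets no age limit. The Setting section describes a hospital on which the province depends for most of its care.

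Patients are identified through the registration form (PRTF). Under Pre-intervention, "the PRTF will require the treating clinician to indicate whether the patient had one of the ten sentinel conditions". The same section says the form will "capture relevant data items, such as demographics and initial vital signs (Appendix 1").

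The ten conditions define the cohort for time to assessment and for the proportion seen within 15 minutes. The mortality calculation uses the same 15 sentinel patients per day. The Limitations section acknowledges that acuity may change once triage starts and answers: "For this reason, the primary outcome will focus on ten clearly-defined time critical conditions".

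**The concern.** A systolic pressure at or a little below 90 mmHg can be normal in a young child. That is general physiology, not a figure in the documents. Read literally, the rule classes a toddler with a minor fever and a pressure of 88 mmHg as septic shock. For pneumonia and asthma/COPD, the physiological sign must be accompanied by a leading diagnosis. For septic shock, the two vital signs are enough.

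Two things are at stake. First, patients who are not time-critical dilute the cohort: they would be expected to die rarely, and a triage scale may have no reason to bring them forward. Second, in an uncontrolled pre-post comparison the condition list is the plan's stated protection against changing acuity. If one condition can be met by children who are not in shock, and their share differs between periods, part of any difference would reflect who was counted.

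**Working it through.** **1. The text.** Five features were compared.

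- Cut-off: one value for all ages (Appendix 3).
- Diagnostic clause: present for four conditions, absent for septic shock (Appendix 3).
- Age limit: none stated.
- Entry: the treating clinician marks the condition (Pre-intervention).
- Use: primary outcome, 15-minute proportion and mortality (Outcomes, Sample size).

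So a febrile child with pressure normal for age can meet the definition. Meeting it leads to entry only if the clinician marks it.

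**2. The plan's own sample sizes.** The formula uses pooled variance, two-sided alpha 0.05 and power 0.80 (the plan writes this as beta of 0.8), without continuity correction:

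n per group = [1.960·√(2p̄(1−p̄)) + 0.842·√(p₁(1−p₁) + p₂(1−p₂))]² / (p₁ − p₂)²

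- Mortality, "from an estimated baseline mortality rate of 15"% to 10%: p̄ = 0.125; (0.9167 + 0.3925)² / 0.0025 = 685.6, so 686 per group and 1372 in total. This matches the plan.
- Seen within 15 minutes, 45% to 55%: p̄ = 0.50; (1.3859 + 0.5921)² / 0.01 = 391.3, so 392 per group and 784 in total. This matches the plan.

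**3. Patients per period.** 15 per day × 56 days = 840.

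**4. Dilution.** Let f be the share of the cohort misclassified. The documents do not give f, so a range is shown. Two assumptions are made: misclassified patients have no deaths, giving rates of 15%·(1−f) and 10%·(1−f); and they stay at 45% seen within 15 minutes in both periods, giving a post-intervention rate of 55%·(1−f) + 45%·f.

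| f | Mortality rates | n per group | Power at 840 | 15-minute rates | n per group | Power at 840 |
|---|---|---|---|---|---|---|
| 0 | 15.0% v 10.0% | 686 | 87% | 45% v 55.0% | 392 | 98% |
| 5% | 14.25% v 9.5% | 727 | 85% | 45% v 54.5% | 434 | 97% |
| 10% | 13.5% v 9.0% | 773 | 83% | 45% v 54.0% | 484 | 96% |
| 20% | 12.0% v 8.0% | 882 | 78% | 45% v 53.0% | 612 | 91% |

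The table holds the cohort at 840, so each misclassified child displaces a true case. If the children come on top of the planned 15 per day, the loss is smaller. At f = 10% the cohort would be 840/0.9 = 933 against 773 required (ratio 1.21), compared with 840 against 686 (ratio 1.22) at f = 0.

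**5. How easily the cut-off is met.** The documents give no blood-pressure distribution. If young children's systolic pressure is normal with mean 85 to 100 mmHg and SD 10 (assumed), the share at or below 90 runs from Φ(0.5) = 69% to Φ(−1.0) = 16%. This shows that the overlap is not a marginal case. It does not give f, which also needs the number of children seen, the share febrile, whether pressure is measured, and whether the clinician marks septic shock.

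**The case against.** The strongest counter-argument is that vital signs do not place anyone in the cohort automatically. A clinician has to mark septic shock, and one who judges a toddler to be well may not do so, whatever the pressure. Appendix 3 is offered as a set of pragmatic definitions. The forms and the WHO scale guidance are attachments that are not in the text reviewed, and they may say how to apply the definitions to children. This stands, and it limits the point to children who could meet the definition. It does not remove the point: if clinicians override the written rule by judgement, the condition is less clearly defined than the Limitations section assumes.

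A reader might go further and infer a spurious fall in mortality. Suppose 0.5 such children per day are counted before and 3 per day after, because pressure is recorded more often, with 1% mortality among them and 15% among the 15 true cases. Mortality would move from (2.25 + 0.005)/15.5 = 14.5% to (2.25 + 0.03)/18 = 12.7%, about 1.9 points of the planned 5. The documents do not support this. Every input is assumed, and the form captures initial vital signs in both periods, so nothing in the text suggests a sixfold rise. The sum also has no term for the clinician's decision: if 10% to 50% of these children were marked (assumed), the artefact would be about 0.2 to 1.0 points.

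It is also tempting to extend the point to "raised troponin based on the threshold defined by the local laboratory" for myocardial infarction, which likewise has no diagnostic clause. Entry there too depends on the clinician's mark, and no effect on the results has been shown, so it is not part of this point.

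**Conclusion.** The point holds as a weakness in a cohort definition. As written, the septic shock criterion can be met by febrile young children whose pressure is normal for age, and nothing else in the available text excludes them except the individual clinician's judgement. This weakens the safeguard that the plan itself names against case-mix change.

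The number affected cannot be derived from the documents. At modest levels the cost in power is small: under the stated assumptions, mortality power with 840 per period falls from about 87% to 83% at 10% misclassified and 78% at 20%, and power for the 15-minute proportion stays above 90%. The sample sizes of 1372 and 784 reproduce and are not in question. A reader might infer that these children necessarily enter the cohort, or that they would manufacture a mortality benefit. The first ignores the clinician's mark, and the second is hypothetical. Any dilution of the time-to-assessment effect also assumes that the triage scale would not prioritise these children, which cannot be checked without the attached guidance.

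**What to change.** Before baseline data collection, make two changes to the septic shock entry in Appendix 3.

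1. Make the hypotension criterion depend on age, with bands chosen and fixed by the investigators. State the age range that the study covers. No threshold is proposed here.
2. Add a clause built like the pneumonia one, requiring septic shock to be the treating clinician's leading diagnosis. A clause asking only for infection would not be enough, because a toddler with a minor fever would often satisfy it.

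If the form cannot be changed, prespecify in the analysis that a child marked as septic shock is counted only if the recorded systolic pressure is below the investigators' age-specific cut-off. The demographics and initial vital signs on the form should allow this, provided that age is among the demographics.

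The cost is a short edit to Appendix 3, and slightly fewer patients may be counted as septic shock. The rule still depends on blood pressure being recorded, so the share with a recorded value should be reported by period. The change concerns cohort classification only and leaves patient care as it is.
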